2.4.5 Analyses of safety data

The safety of long-term tolebrutinib treatment will be presented by SAR dose group (5/60, 15/60, 30/60, and 60/60 mg) and overall. in the safety population. Selected summaries will be included for Part A only to assess for any dose related trends in adverse events. If average exposure across the dose groups is very different, exposure adjusted summaries will be considered.

General common rules

All safety analyses will be performed on the LTS16004 safety population, unless otherwise specified, using the following common rules:

- The baseline value of planned parameters for each participant is defined as the last available value before the first study drug intake in DRI15928 whether it was a planned or an unscheduled evaluation, unless otherwise specified.
- The potentially clinically significant abnormality (PCSA) values are defined as abnormal values considered medically important by the Sponsor according to predefined criteria/thresholds based on literature review and defined by the Sponsor for clinical laboratory tests, vital signs, and ECG.
- PCSA criteria will determine which participants had at least 1 PCSA during the on-treatment period, taking into account all evaluations performed, including nonscheduled or repeated evaluations. The number of all such participants will be the numerator for the PCSA percentage.
- The on-treatment PCSA denominator by dose group for a given parameter will be based on the number of participants assessed for that given parameter in the on-treatment period by dose group on the safety population.
- For quantitative safety parameters based on central laboratory/reading measurements, descriptive statistics will be used to summarize results and change from baseline values by visit and dose group.
- All values including unscheduled measurements will be assigned to the appropriate safety analysis visit window. In the presence of multiple measurements of the same test in the same window, the one closest to the targeted visit date will be used for the by-visit summaries.
- The analysis of the safety variables will be descriptive; no systematic testing is planned.

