1.6 STATISTICAL MODIFICATIONS MADE IN THE STATISTICAL ANALYSIS PLAN

SAP Version	Approval Date	Changes	Rationale
2	10-Jul-2023	Changed SAR442168 to tolebrutinib throughout. Added opportunity to enroll in Phase 3 LTS17043 after completing the current study.	Subsequent availability of the INN - international nonproprietary name could be added to abbreviations. Since the LTS16004 study will end in 2024 and the phase 3 LTS is scheduled to start in 2024, participants will have the opportunity to continue tolebrutinib treatment.

SAP Version	Approval Date	Changes	Rationale
		Deleted study schedule and graphical study design.	They are already detailed in the protocol and so replaced with a reference to the protocol sections.
		Added missing MRI parameters as efficacy endpoints and the corresponding analysis methods.	Several exploratory MRI parameters were missed in the previous SAP version.
		Added safety findings on MRI to safety endpoints. Added the contents about reporting of safety findings from MRI.	Based on Protocol Amendment 02 & 05.
		Added summary tables for AEs occurring in Part A only.	To assess for any dose relationship in adverse events in Part A.
		Extended disposition summary.	To cover treatment and study status in both parts (A and B) of the study.
		Removed the miTT DRI15928+LTS16004 population in Section 2.3.1	Considering that miTT LTS16004 population is already defined and that there is no difference between these two populations.
		Added supplementary analysis of ARR on 60 mg tolebrutinib including data from all dose groups after the switch to the 60 mg dose.	Since all participants switch to tolebrutinib 60 mg in Part B, a better estimate of the ARR at this dose level can be provided by grouping participants together.
		Added a summary of COVID-19 related AEs in Section 2.4.5.1	Grouping PTs to get the overall incidence of COVID-19.
		Added methods of addressing missing data issue due to regional or national emergency.	According to Protocol Amendment 04.
		Added a table describing the selection criterion for each AESI category	To give a more explicit description of all AESI categories and to be aligned with the SAPs of the tolebrutinib phase 3 studies.
		Reformatted existing content when necessary. Did minor, editorial, stylistic changes as necessary. Updated table of contents, section numbers, abbreviations as necessary.	Accordance with Sponsor's standards.

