2.1.4 Safety endpoints

The safety analyses will be based on the reported AEs, including safety findings on MRI, and other safety information, such as clinical laboratory, ECG, vital signs, and C-SSRS data collected in LTS16004.

Magnetic resonance imaging scans should be reviewed locally for any non-MS pathology. In case of such findings, the relevant information needs to be provided to the Investigator for appropriate safety reporting and to ensure the appropriate management of the participant's identified safety finding. When available, a diagnosis of pathology as a cause of such MRI findings or the findings themselves will be reported as an AE until the diagnosis is clear.

MS relapses are exempt from being reported as AE/SAE unless, in the judgment of the Investigator, it is unusually severe or medically unexpected. MS relapses are collected on the eCRF and analyzed as part of the efficacy analyses.

Observation periods

In general, there should be no pretreatment AEs in the LTS16004 study since participants were to roll directly into LTS16004 after completing the DRI15928 study. However, in case there is a gap, the pre-treatment period for the LTS16004 study is defined as the time from signing the ICF until first IMP intake in the LTS16004 study.

The on-treatment period is from first administration of tolebrutinib in the LTS16004 study to the last administration +10 days, including both Part A and Part B treatment periods.

The post-treatment period, if applicable, is from the end of the on-treatment period to the end of the follow-up in LTS16004.

The on-study period is from signing the ICF to the end of follow-up in the LTS16004 study.

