ARR will be analyzed using a negative binomial regression model in the mITT population. The model will include the total number of confirmed relapses with onset between first and last IMP doses in LTS16004 as response variable and dose group (5/60, 15/60, 30/60, and 60/60 mg) as covariate. Log transformed standardized treatment duration will be included in the model as an "offset" variable. The estimated ARR for each dose group and corresponding 95% 2-sided CI will be derived from the negative binomial model. The relative reductions in ARR (60/60 mg versus each other dose group) along with 95% CIs will be estimated from the model.

Number of participants with 0, 1, 2, 3, 4, or ≥ 5 relapses will be presented by dose group, namely, 5/60, 15/60, 30/60, and 60/60 mg.

The ARR for the tolebrutinib 60 mg treatment period will be analyzed using a negative binomial regression model, as well. Only relapses with onset during the tolebrutinib 60 mg treatment period will be counted, which means Part B only for participants originally assigned to 5, 15 and 30 mg dose groups and Parts A and B for participants originally assigned to the 60 mg dose group. Excluded are patient years and relapses during the first 8 weeks of tolebrutinib treatment after the switch to Part B for participants in the 5/15/30 to 60 mg groups and the same for participants in the 60/60 mg dose group, if the sum of the placebo run-out period (if applicable) and any gap period is >4 weeks. The negative binomial regression model will use total number of relapses as the response variable and log transformed standardized treatment duration as an "offset" variable. The estimated ARR and the 95% CI will be provided.

The number of participants with 0, 1, 2, 3, 4, or ≥ 5 relapses during the tolebrutinib 60 mg treatment period will also be presented.

Proportion of participants relapse free

Time to first confirmed relapse in LTS16004 is defined as "the date of first relapse - first IMP date (in LTS16004) + 1". If the participant has no relapse before treatment discontinuation/completion, then the participant will be considered as free of relapse until the date of treatment discontinuation/completion. His/her data will be censored after this date. The proportion of participants without confirmed relapse in LTS16004 will be estimated based on the Kaplan-Meier curve at yearly time points (1, 2, 3, 4 and 5 years since first IMP in LTS16004).

Change from baseline in EDSS scores

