2.4.5.1 Analyses of adverse events

Generalities

If an AE date/time of onset (occurrence or worsening) is incomplete, an imputation algorithm will be used to classify the AE as pre-treatment, TEAE or posttreatment. The algorithm for imputing date/time of onset will be conservative and will classify an AE as treatment emergent unless there is definitive information to determine it is pre- or post-treatment.

Adverse event incidence tables will present by primary SOC and PT, the number (n) and percentage (%) of participants experiencing an adverse event by tolebrutinib dose group, and overall. Multiple occurrences of the same event in the same participant will be counted only once in the tables. The denominator for computation of percentages is the safety population within each dose group/overall.

Summaries by primary SOC and PT will be presented by internationally agreed order of SOC and decreasing frequency of PT in the 60/60 mg tolebrutinib dose group within each SOC. Summaries by PT will be sorted by decreasing frequency of PT in the 60/60 mg tolebrutinib dose group.

Selected summaries (noted with an * below) will also be provided for Part A only. These tables will summarize incidence of adverse events by tolebrutinib dose group, namely, 5, 15, 30, and 60 mg, sorted by decreasing frequency in the tolebrutinib 60 mg dose group.

Analysis of all treatment-emergent adverse events

The following treatment-emergent adverse event summaries will be generated for the safety population:

- Overview* of treatment-emergent adverse events, summarizing number (%) of participants with any.
 - TEAE.
 - Treatment emergent SAE.
 - Severe TEAE.
 - AE leading to death.
 - TEAE leading to permanent treatment discontinuation.
 - TEAE considered by the investigator as related to IMP.
- All TEAEs by primary SOC and PT*.
- All TEAEs by PT.
- All TEAEs considered related to IMP (by the investigator) by primary SOC and PT.
- All TEAEs (for which intensity is collected) by maximal intensity (mild, moderate, severe), presented by primary SOC and PT.

Analysis of all treatment emergent serious adverse event(s)

- All treatment emergent SAEs by primary SOC and PT*.
- All treatment emergent SAEs by PT.
- All treatment emergent SAEs considered related to IMP (by the investigator) by primary SOC and PT.
- Listing of all SAEs including treatment emergent status.

Analysis of all treatment-emergent adverse event(s) leading to treatment discontinuation

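### The SAP commits to no exposure-adjusted AE rate and to no AE summary covering all participants' 60 mg treatment time

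*SAP*

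**What the plan says.** SAP 2.1.4 defines one on-treatment period, from the first LTS16004 dose "to the last administration +10 days, including both Part A and Part B treatment periods". SAP 2.4.5 sets the columns: "The safety of long-term tolebrutinib treatment will be presented by SAR dose group (5/60, 15/60, 30/60, and 60/60 mg) and overall".

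SAP 2.4.5.1 makes the measure a count and percentage of participants. "The denominator for computation of percentages is the safety population within each dose group/overall", and "Multiple occurrences of the same event in the same participant will be counted only once in the tables". On splitting by part it says: "Selected summaries (noted with an * below) will also be provided for Part A only". Those tables use the actual Part A doses of 5, 15, 30 and 60 mg. No matching table is listed for Part B or for time on 60 mg. The one sentence on exposure, in SAP 2.4.5, is: "If average exposure across the dose groups is very different, exposure adjusted summaries will be considered". It gives no threshold and no method.

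Relapses are treated differently. SAP 2.4.4 defines a 60 mg treatment period: Part B for those who started on 5, 15 or 30 mg, and both parts for those who started on 60 mg. "Only relapses with onset during the tolebrutinib 60 mg treatment period will be counted", with log treatment duration as an offset. SAP 1.6 gives the reason: "a better estimate of the ARR at this dose level can be provided by grouping participants together".

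**The concern.** Part B exists to give long-term safety data at the selected dose (Protocol 4.2), and everyone who enters it takes 60 mg. Yet no planned AE table isolates that experience. In three of the four sequence columns, and in the overall column, an event on 5, 15 or 30 mg falls in the same cell as an event on 60 mg. The Part B count cannot be recovered by subtracting the Part A table, because a participant with the same event in both parts is counted once in the total.

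The conditional sentence does not close the gap. Four groups with similar average exposure would never trigger it, yet dose would still change within person and follow-up would still differ between individuals over up to five years.

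The period after the switch is of particular interest. Protocol 2.3 reports drug-induced liver injury in the Phase 3 trials in Months 1 to 3 after treatment start. Those who began on lower doses, about three quarters of participants, first receive 60 mg at the switch to Part B, and no planned summary isolates AEs from that point.

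**Working it through.** The documents state no sample size, power or AE rate, so there is no figure to reproduce. The size is shown by person-time arithmetic.

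**Inputs**
- Enrolled: 126 (SAP 1.3).
- Month 60: day 1680 (SAP 2.5.3, Table 2; 28-day months), so 1680/365.25 = 4.60 years.
- Equal allocation to four dose groups in DRI15928 (Protocol 6.3). An even split of the 126 is an assumption: 31.5 per group, with 3 × 31.5 = 94.5 starting below 60 mg.
- Part A length: not given, so varied over 12 to 52 weeks. Protocol 6.3 calls it unlikely that DRI15928 plus Part A exceeds a year. With a Week 16 visit in DRI15928 (Protocol 1.3, Table 1, footnote a), 52 − 16 = 36 weeks is a reasonable central case.
- Everyone followed to Month 60 (assumption).

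**Share of exposure below 60 mg**
- Each of the 5/60, 15/60 and 30/60 columns: Part A days/1680. 12 weeks: 84/1680 = 5%. 36 weeks: 252/1680 = 15%. 52 weeks: 364/1680 = 21.7%.
- Overall column: three quarters of that, or 3.7%, 11.3% and 16.3%.
- 60/60 column: 0%.

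**Participant-years (PY) at 60 mg**
- Total: 126 × 4.60 = 579.5.
- 60/60 only: 31.5 × 4.60 = 144.9.
- All 60 mg time: 579.5 − 94.5 × Part A years. 12 weeks: 579.5 − 94.5 × 0.230 = 557.8. 52 weeks: 579.5 − 94.5 × 0.997 = 485.4.
- Ratio to 60/60 alone: 3.85 to 3.35.
- Carrying over the 8-week exclusion used for relapses would remove 94.5 × 56/365.25 = 14.5 PY, leaving 543.3 to 470.9.

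**What that buys.** With zero events, the exact one-sided 95% Poisson upper bound is −ln(0.05)/PY = 2.996/PY.
- 60/60 only: 2.996/144.9 = 2.07 per 100 PY.
- All 60 mg time: 2.996/557.8 = 0.54 to 2.996/485.4 = 0.62 per 100 PY.
- As proportions, 1 − 0.05^(1/n): about 9% for n = 31 or 32, and 2.3% for n = 126.

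**Dilution, illustrated.** Suppose an AE occurs at 10 per 100 PY on 60 mg and 5 per 100 PY below it, with a 48-week (0.92-year) Part A; all three figures are assumed.
- Switcher columns: 1 − exp(−(0.05 × 0.92 + 0.10 × 3.68)) = 33.9%.
- 60/60 column: 1 − exp(−0.10 × 4.60) = 36.9%.
- Overall: 0.75 × 33.9% + 0.25 × 36.9% = 34.6%. The overall rate is 9.25 rather than 10 per 100 PY.

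**The case against.** A reader might infer that the study will yield no AE incidence at 60 mg. The documents do not support that. The 60/60 group takes 60 mg throughout, so its column is pure 60 mg incidence over the whole study, and the Part A tables have their own 60 mg column.

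Nor is heavy contamination supported. A Part A long enough to put 30% of switcher exposure below 60 mg would need 72 weeks (504/1680), against the expectation in Protocol 6.3. The illustrated distortion is a few percentage points.

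The SAP also does what the protocol asks. The objective is safety of the drug, not incidence at one dose; Protocol Table 10 calls for overall descriptive incidence; and no comparison with other 60 mg data is planned. Participant-years are reported by part (SAP 2.4.3.1), and the death and treatment-discontinuation listings show dose or treatment at the time (SAP 2.4.5.2 and 2.2). SAEs, AESIs and TEAEs leading to discontinuation are all listed. The relapse analysis is labelled supplementary in SAP 1.6.

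All of this stands, and it limits the point to a missing summary. It does not remove it. SAP 2.4.3.1 already supplies total 60 mg exposure: Part B participant-years plus the 60 mg group's Part A participant-years. The event counts to go with it are missing. For an event that never occurs, a reader could work out the bound. For one that does occur, the tables do not say whether it began on 60 mg. Listings help with individual cases but are not a prespecified rate.

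**Conclusion.** The point holds as a gap in what is prespecified; no planned table is invalid. The SAP commits to no AE rate per participant-year and to no AE summary of all participants' 60 mg time, and the conditional sentence would not supply either. Mixing of doses is a modest problem: about 5% to 22% of switcher exposure and 4% to 16% of overall exposure. The larger cost is precision, because pure 60 mg incidence is shown for only about a quarter of participants when 3.3 to 3.9 times as much 60 mg exposure is available.

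These figures rest on even groups, full follow-up and a Part A of 12 to 52 weeks. Dropout would lower the participant-years and widen both bounds. The effect of unequal individual follow-up on the crude percentages cannot be sized from the documents. That the summary is absent depends on none of these assumptions.

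**What to change.** Keep the existing tables as planned. Replace the conditional sentence in SAP 2.4.5 with a commitment to add summaries of TEAEs, SAEs, AESIs and TEAEs leading to permanent discontinuation for the 60 mg treatment period: Part B for 5, 15 and 30 mg starters, Parts A and B for 60 mg starters.

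- Assign each event by dose at onset.
- Report n (%) and participants with event per 100 participant-years at risk, with time censored at first event, and a 95% CI.
- State that the 8-week post-switch exclusion used for the relapse rate does not apply to these summaries, since it would discard the early time after the switch.
- Footnote that the pooled rate combines blinded Part A with open-label Part B time.

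The cost is a few extra tables. The 60 mg period is already defined for relapses and exposure is already derived by part, so no new data are needed.

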2.4.5.1 Analyses of adverse events

Generalities

If an AE date/time of onset (occurrence or worsening) is incomplete, an imputation algorithm will be used to classify the AE as pre-treatment, TEAE or posttreatment. The algorithm for imputing date/time of onset will be conservative and will classify an AE as treatment emergent unless there is definitive information to determine it is pre- or post-treatment.

Adverse event incidence tables will present by primary SOC and PT, the number (n) and percentage (%) of participants experiencing an adverse event by tolebrutinib dose group, and overall. Multiple occurrences of the same event in the same participant will be counted only once in the tables. The denominator for computation of percentages is the safety population within each dose group/overall.

Summaries by primary SOC and PT will be presented by internationally agreed order of SOC and decreasing frequency of PT in the 60/60 mg tolebrutinib dose group within each SOC. Summaries by PT will be sorted by decreasing frequency of PT in the 60/60 mg tolebrutinib dose group.

Selected summaries (noted with an * below) will also be provided for Part A only. These tables will summarize incidence of adverse events by tolebrutinib dose group, namely, 5, 15, 30, and 60 mg, sorted by decreasing frequency in the tolebrutinib 60 mg dose group.

Analysis of all treatment-emergent adverse events

The following treatment-emergent adverse event summaries will be generated for the safety population:

- Overview* of treatment-emergent adverse events, summarizing number (%) of participants with any.
 - TEAE.
 - Treatment emergent SAE.
 - Severe TEAE.
 - AE leading to death.
 - TEAE leading to permanent treatment discontinuation.
 - TEAE considered by the investigator as related to IMP.
- All TEAEs by primary SOC and PT*.
- All TEAEs by PT.
- All TEAEs considered related to IMP (by the investigator) by primary SOC and PT.
- All TEAEs (for which intensity is collected) by maximal intensity (mild, moderate, severe), presented by primary SOC and PT.

Analysis of all treatment emergent serious adverse event(s)

- All treatment emergent SAEs by primary SOC and PT*.
- All treatment emergent SAEs by PT.
- All treatment emergent SAEs considered related to IMP (by the investigator) by primary SOC and PT.
- Listing of all SAEs including treatment emergent status.

Analysis of all treatment-emergent adverse event(s) leading to treatment discontinuation

- All TEAEs leading to permanent IMP discontinuation by primary SOC and PT.
- All TEAEs leading to permanent IMP discontinuation by PT.
- Listing of all TEAEs leading to permanent IMP discontinuation.

Analysis of AESIs

- All treatment emergent AESIs by AESI category and PT* sorted by decreasing frequency of PT in the 60 or 60/60 mg dose group within each AESI category.
- Listing of all AESIs by AESI category including treatment emergent status.

Analysis of COVID-19 related AEs

- All treatment emergent COVID-19 related AEs by primary SOC and PT sorted by decreasing frequency of PT in the 60/60 mg dose group within each SOC.
- Listing of all COVID-19 related AEs.

Analysis of pre-treatment/post-treatment adverse events

- Pre-treatment and post-treatment adverse events, if any, including serious, will be summarized separately.
- Listing of all pre-and post-treatment adverse events.

Safety findings on MRI are collected as AEs on the eCRF and will be analyzed in together with other AEs.

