- k At the M60 visit, the participants who have completed the study and remain on SAR442168 may be offered participation in a Phase 3 long-term safety study. Follow-up visit assessment only performed for those participants who are not taking part in the long-term safety study.

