1.3 DETERMINATION OF SAMPLE SIZE

There are no sample size calculations for this long-term extension study.

All participants who completed the DRI15928 study were eligible for enrollment in the LTS16004 study. The Sponsor enrolled 130 participants in the DRI15928 study, 129 completed the study treatment, and 126 enrolled in LTS16004.

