2.3.2 Safety population

Safety population: all participants enrolled in LTS16004 and exposed to IMP during LTS16004, regardless of the amount of exposure.

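### Post-treatment adverse event percentages are by default divided by the whole safety population, including rollover participants who have no post-treatment period in this study

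*SAP*

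**What the plan says.** SAP 2.4.5.1 opens with general rules for adverse event tables. They present "the number (n) and percentage (%) of participants experiencing an adverse event by tolebrutinib dose group, and overall", and the rule for the percentage is: "The denominator for computation of percentages is the safety population within each dose group/overall". SAP 2.4.5 runs every safety analysis on that population unless another is named. Under SAP 2.3.2 it comprises "all participants enrolled in LTS16004 and exposed to IMP during LTS16004, regardless of the amount of exposure"; follow-up after the last dose is not required.

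On post-treatment events, SAP 2.4.5.1 says: "Pre-treatment and post-treatment adverse events, if any, including serious, will be summarized separately". It adds this output: "Listing of all pre-and post-treatment adverse events". No denominator or layout is given for the summary.

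SAP 2.1.4 ends the on-treatment period 10 days after the last administration and continues: "The post-treatment period, if applicable, is from the end of the on-treatment period to the end of the follow-up in LTS16004". In the protocol, footnote k to the Year 5 schedule (section 1.3, Table 3) concerns participants who reach Month 60 on drug and may enter the Phase 3 long-term safety study: "Follow-up visit assessment only performed for those participants who are not taking part in the long-term safety study".

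For everyone else, follow-up depends on where one looks. Table 3 places the follow-up visit 8 weeks after the last dose. Footnotes to all three schedule tables bring participants back 4 to 6 weeks after premature end of treatment. Protocol 7.1.1 follows participants who stop definitively to the scheduled completion date or until an adverse event has settled, whichever is later.

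**The concern.** A percentage is informative when everyone in its denominator could have had the event recorded. That is true of treatment-emergent events, because every member of the safety population was dosed. It is not true of post-treatment events. A participant who rolls over at Month 60 leaves LTS16004 with no follow-up visit, contributes no post-treatment observation, and still adds one to the denominator. The percentage then falls as rollover uptake rises, whatever happens to those who stop.

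The table is also planned by dose group. If rollover differs between groups, the percentages differ even where the proportion affected among observable participants is the same.

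A second weakness concerns time. Participants with a post-treatment period are observed for very unequal lengths, and nothing in the summary shows how long. The only adjustment the SAP mentions (2.4.5) is to be considered if average exposure differs greatly across dose groups. That concerns time on drug, not time after it.

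**Working it through.** **No planned figure to reproduce.** The documents state no post-treatment percentage and no number rolling over. The check derives the size as a function of the unknown share.

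**Inputs**

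- N: at most 126. SAP 1.3: "129 completed the study treatment, and 126 enrolled in LTS16004". The safety population cannot exceed the number enrolled.
- r: the share of the safety population with no post-treatment period. Not given; rollover is optional.
- End of on-treatment period: last dose + 10 days (SAP 2.1.4).
- Follow-up visits: 4 to 6 weeks after premature end of treatment, or 8 weeks after the last dose (protocol 1.3).
- 1 month = 28 days, so Month 60 is day 1680 (SAP 2.5.3).

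**Step 1: dilution.** Let a participants have a post-treatment event.

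- Planned percentage = a / N
- Percentage among those observable = a / [N(1 − r)]
- Ratio of the second to the first = 1 / (1 − r)

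Illustration with a = 5, an assumed count: the planned percentage is 5/126 = 4.0%, whatever r is.

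| r (assumed) | Observable, 126(1 − r) | Factor 1/(1 − r) | 5 / observable |
|---|---|---|---|
| 0% | 126 | 1.0 | 4.0% |
| 25% | 94.5 | 1.33 | 5.3% |
| 50% | 63 | 2.0 | 7.9% |
| 75% | 31.5 | 4.0 | 15.9% |

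Fractional participants are kept so that the percentages match the factor exactly. A 3-fold dilution needs 1 − r ≤ 1/3, that is, r of at least 67%.

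**Step 2: between dose groups.** If two groups had the same percentage among observable participants but r of 50% and 75%, their planned percentages would differ by (1 − 0.50)/(1 − 0.75) = 2-fold.

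**Step 3: post-treatment time at risk.** This is the end of follow-up minus (last dose + 10 days).

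- Rollover participants: no observation in LTS16004.
- 4-week visit: 28 − 10 = 18 days. 6-week visit: 42 − 10 = 32 days. Both assume that the visit is dated from the last dose.
- 8-week visit: 56 − 10 = 46 days (36 to 56 with the ±10-day window).
- Stopping at Month 1 and followed to Month 60 under protocol 7.1.1: 1680 − 28 − 10 = 1642 days, and 1642/365.25 = 4.5 years.

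**Step 4: what unequal time does to a crude percentage.** Assume, for illustration only, a constant rate of 0.5 first events per participant-year. The expected proportion affected, 1 − exp(−0.5 × days/365.25), is 2.4% at 18 days, 4.3% at 32, 6.1% at 46 and 89.4% at 1642. A crude percentage over such a mixture mainly reflects who was followed and for how long.

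**The case against.** That the general denominator governs the post-treatment summary is an inference. The SAP says only that these events are summarized separately; unlike the treatment-emergent bullets, it promises neither a layout nor a percentage, and it recognises that the period may not apply to everyone. This stands as a caveat. But SAP 2.4.5 makes the safety population the default for all safety analyses, and nothing displaces it here, so a programmer following the text would use it.

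The harm is modest, and this stands too. The table is ancillary and descriptive, no p-values are planned, counts appear beside percentages, and every post-treatment event is listed. In a study of at most 126 participants no event is hidden. Dividing by the safety population is also a common convention. These points limit the harm but do not remove the defect: neither counts nor an event listing shows how many participants were observable or for how long. The SAP already follows the better principle for potentially clinically significant abnormalities (2.4.5), where the denominator is those assessed for the parameter in the period.

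Part of the spread in follow-up time comes from the protocol rather than the SAP. The 4-to-6-week visit and follow-up to scheduled completion apply to overlapping participants and are not reconciled, so the multi-year figure is possible rather than certain.

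A reader might infer that incidence will be understated several-fold. The documents do not support that. Rollover is optional and open only to those who complete Month 60 on drug, and five years of discontinuations reduce it. Uptake into the present extension was high (126/129 = 97.7%), but that was a different transition and is no estimate of r. A reader might also suppose that the table exists to measure the effects of stopping the drug; no such objective appears in the text available.

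**Conclusion.** The point holds as a correctable flaw in one set of descriptive tables. Under the default rule the planned post-treatment percentage is too low whenever some of the safety population has no post-treatment period, by a factor of 1/(1 − r). The mechanism is well supported; the size is not known, because r is not in the documents and the effect vanishes at r = 0. The conclusion rests on two readings: that the general denominator applies where none is named, and that a rollover participant's observation in LTS16004 ends without post-treatment follow-up. The documents do not state that rollover involves no gap in dosing, but without a follow-up visit such a gap would not be observed in this study. The unequal follow-up time is a second, separate reason why a crude percentage is hard to interpret.

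**What to change.** In SAP 2.4.5.1, state that the denominator for the post-treatment adverse event summary is the number of participants, in each dose group and overall, with at least 1 day of post-treatment follow-up. Show that number and the total post-treatment person-time beside the counts. A fixed window to 8 weeks after the last dose would not be enough by itself, since it would still mix participants last seen at 4 to 6 weeks with those seen at 8.

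Reconcile the 4-to-6-week follow-up visit in the schedule of activities with follow-up to scheduled completion in protocol 7.1.1, because together they define the post-treatment time at risk.

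The SAP change costs a sentence or two of wording and a revised denominator, with person-time added, in one table set. It needs no new data collection. The protocol point needs a clarification of which follow-up applies to whom.
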